### **6.2 RESPONSE CRITERIA**

Follow up MRI of the pelvis at day 0, 1 and at 0.5, 1, 2, and 3 years. The targeted lesions on MRI should demonstrate changes consistent with successful treatment (a decrease of enhancement on MP MRI). (Scans can be obtained within +/- 1 month of the target time table)

Follow up systematic core biopsy of the prostate at 1, 2, and 3 (optional) years showing no evidence of invasive prostate cancer in the region of laser ablation. (Biopsies can be obtained within +/- 1 month of the target time table)

Standard and MR image guided biopsy of previous laser ablation sites should show no evidence of cancer.

Follow up DRE and physical exam at 3, 6, 12, 18, 24 months and 3 years. This should show no palpable disease, if disease is detected then further workup with one of the above mentioned tests will be performed.

### 6.3 TOXICITY CRITERIA

The following adverse event management guidelines are intended to ensure the safety of each patient while on the study. The descriptions and grading scales found in the revised NCI Common Terminology Criteria for Adverse Events (CTCAE) version 4.0 will be utilized for AE reporting. A copy of the CTCAE version 4.0 can be downloaded from the CTEP web site ([http://ctep.cancer.gov/protocolDevelopment/electronic\\_applications/ctc.htm](http://ctep.cancer.gov/protocolDevelopment/electronic_applications/ctc.htm)). All appropriate treatment areas should have access to a copy of the CTEP Active Version of CTCAE.

There currently is no large series of data regarding laser ablation of the prostate. Large series of focal laser ablation of solid tumors reports an overall complication rate of 1.5% and a 30 day mortality rate of 0.1%. Trachtenberg et al reported a series of 12 patients. There were no mortalities and the complication rates reported were as follows: Postoperative morbidity was minimal, self-limited and required no intervention. Perineal discomfort was the most common side effect (25% of patients). Two patients had mild hematuria that did not require any intervention and cleared spontaneously, 2 patients had hematospermia and 1 had fatigue. Due to the limited paucity of information we will also in cooperate and follow data points from the focal cryoablation data (table below).

Table 2 – Complications (%) after primary cryosurgery

Ref.	No. patients	Technique	Fistula	Slough	Retention	Incontinence	Impotence	UTI	Perineal pain
Long et al. [16]	975	LN/Ar	0.4	NA	10	7.5	30	NA	NA
Donnelly et al. [17]	76	LN	NA	3.9	NA	1.3	100 (33: =3 yr)	NA	NA
Bahn et al. [15]	590	LN/Ar	0.004	NA	5.5	4.3	35	NA	NA
Ellis et al. [25]	75	Ar	0	6.7	6.7	5.4	82	NA	NA
Han et al. [12]	122	Ar	0	4.9	NA	3	87	NA	6
Prepelica et al. [28]	65	Ar	0	NA	5.1	3.1	NA	NA	1.1
Jones et al. [29]	1198	LN/Ar	0.4	NA	NA	2.9	31	NA	NA
Hutbosky et al. [30]	89	Ar	1	2	4	2	NA	1	6

UTI, urinary tract infection; NA, not available; LN, liquid nitrogen; Ar, argon gas.

## 7 SAFETY REPORTING REQUIREMENTS/DATA AND SAFETY MONITORING PLAN

### 7.1 DEFINITIONS

#### 7.1.1 Unanticipated Adverse Device Effect

Unanticipated adverse device effect is any serious adverse effect on health or safety, any life-threatening problem or death caused by, or associated with a device, if that effect, problem, or death was not previously identified in nature, severity, or degree of incidence in the application; or any other unanticipated serious problem associated with a device that relates to the rights, safety, or welfare of subjects.

All adverse device effects will be followed until return to baseline or stabilization of event. Unanticipated adverse device effects that occur more than 30 days after the last administration of investigational agent/intervention should be recorded and reported as per section 7.2.

### **7.1.2 Serious**

An Unanticipated Problem or Protocol Deviation is serious if it meets the definition of a Serious Adverse Event or if it compromises the safety, welfare or rights of subjects or others.

### **7.1.3 Protocol Deviation (NIH Definition)**

Any change, divergence, or departure from the IRB-approved research protocol.

### **7.1.4 Non-compliance (NIH Definition)**

The failure to comply with applicable NIH Human Research Protections Program (HRPP) policies, IRB requirements, or regulatory requirements for the protection of human research subjects.

### **7.1.5 Unanticipated Problem**

Any incident, experience, or outcome that:

- Is unexpected in terms of nature, severity, or frequency in relation to
  - (a) the research risks that are described in the IRB-approved research protocol and informed consent document; Investigator's Brochure or other study documents, and
  - (b) the characteristics of the subject population being studied; **AND**
- Is related or possibly related to participation in the research; **AND**
- Suggests that the research places subjects or others at a *greater risk of harm* (including physical, psychological, economic, or social harm) than was previously known or recognized.

## **7.2 NCI-IRB AND CLINICAL DIRECTOR REPORTING**

### **7.2.1 NCI-IRB and NCI CD Expedited Reporting of Unanticipated Problems and Deaths**

The Protocol PI will report in the NIH Problem Form to the NCI-IRB and NCI Clinical Director:

- All deaths, except deaths due to progressive disease
- All Protocol Deviations
- All Unanticipated Problems
- All non-compliance

Reports must be received within 7 days of PI awareness via iRIS.

## **7.2.2 NCI-IRB Requirements for PI Reporting at Continuing Review**

The protocol PI will report to the NCI-IRB:

1. A summary of all protocol deviations in a tabular format to include the date the deviation occurred, a brief description of the deviation and any corrective action.
2. A summary of any instances of non-compliance
3. A tabular summary of the following adverse events:
  - All Grade 2 **unexpected** events that are possibly, probably or definitely related to the research;
  - All Grade 3 and 4 events that are possibly, probably or definitely related to the research;
  - All Grade 5 events regardless of attribution;
  - All Serious Events regardless of attribution.

**NOTE:** Grade 1 events are not required to be reported.

## **7.2.3 Non Reportable Occurrences secondary to the MRI or prostate biopsy.**

Patients may have events which we would not consider to be secondary to the laser treatment and therefore not reportable to the IRB. First, the MRI with gadolinium, there is a very low possibility they may develop an acute allergic reaction to the gadolinium, because the patients underwent the MR for the entry process to be screened for the study.

Second, the prostate biopsies performed on the NIH protocol 05-CC-0091 with tissue and specimens acquired on the 97-C-0147 protocol. The patients may develop symptoms post biopsy: Urinary Frequency, Urinary Retention, Dysuria, Hematuria, Erectile Dysfunction, Urinary Tract Infection or Urosepsis post biopsy, which we believe would not be reportable or included in the stopping criteria for the study since these symptoms are not attributed to the laser ablation, especially at the one year and two year biopsy timepoints.

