## **8 STATISTICAL SECTION**

The primary goal of this study is to assess the toxicity, performance and feasibility of the Visualase thermal therapy procedure for focal prostate cancer treatment and then to monitor any complications for the 3 years following treatment. The outcome measures of importance during the thermal treatment are pain, frequency of thermal damage outside of intended treatment areas as measured by post contrast MRI, frequency of not completing the entire procedure, or the frequency of other adverse events and complications. These outcome measures are further defined as follows:

- \* Observing thermal damage on post contrast MRI which extends into areas of the Rectum or Urethra will be considered side effects for stopping purposes.
- \* Frequency of not completing the procedure. Not completing the procedure for reasons other than those given above will be considered a side effect for stopping purposes.
- \* Other adverse events or complications that occur that are classified as Grade 3 or 4 by the National Cancer Institute's Common Toxicity Criteria 4, will be considered a side effect for stopping purposes.

Sample size

The purpose of the study is to assess the safety, performance and feasibility of the Visualase thermal therapy procedure for focal prostate cancer treatment. The sample size is targeted at 15 evaluable patients which is adequate to assess the toxicity rate and can be reasonably recruited in a 6-month period of time. With the accrual of 15 patients, the width of the 80% expected confidence interval of 0.1 and 0.2 toxicity rate is 0.19 and 0.26, respectively.

Stopping rule

For the purpose of protecting patient safety, we implement the following stopping rule for safety monitoring. If one patient experiences a grade 5 event, thought to be possibly or probably due to the laser therapy, the study will be stopped. For grade 3 or 4 event, the study will be stopped according to the following stopping rule.

Number of patients	No. of grade 3 or 4 serious adverse events
3-5	3
6-10	4
11-15	5

The operating characteristic of the stopping rule was assessed by simulations. Based on 10,000 simulations, the probability of stopping early for an excess of serious adverse event over the course of trial is 0.023 when the serious adverse event rate is 0.1 and 0.81 when the serious adverse event rate is 0.40. This is deemed reasonable for protecting patient safety.

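### Section 7.2.3 exempts seven post-biopsy event types from IRB reporting and from the stopping count by type alone, which contradicts 7.2.2 and is not reconciled with Section 8

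*Combined protocol and SAP*

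**What the plan says.** Section 7.2.3 deals with events that the investigators would put down to the MRI or the biopsy. For biopsy it names urinary frequency, retention, dysuria, hematuria, erectile dysfunction, urinary tract infection and urosepsis, "which we believe would not be reportable or included in the stopping criteria for the study". The reason given is attribution: "since these symptoms are not attributed to the laser ablation, especially at the one year and two year biopsy timepoints".

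The neighbouring sections read differently:

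- 7.2.2 (continuing review) asks for "All Grade 5 events regardless of attribution" and "All Serious Events regardless of attribution".
- 7.2.1 (expedited, 7 days) asks for "All deaths, except deaths due to progressive disease".
- Section 8 gives as part of the primary goal to "monitor any complications for the 3 years following treatment". It counts for stopping "Other adverse events or complications that occur that are classified as Grade 3 or 4", with no attribution condition. Its stopping rule ties only grade 5 events to a suspected link with the laser. It does not refer to 7.2.3.
- Section 9.7 lists erectile dysfunction, inability to urinate and blood in the urine among the risks of the ablation itself.

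**The concern.** The exemption works by event type. A listed event that follows a biopsy is presumed unrelated to the laser, whatever its grade and without anyone having to judge the case. The word *post* has no length attached, and singling out the one- and two-year biopsies emphasises those visits without confining the rule to them.

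Two things are at stake. First, a site that follows 7.2.3 as written would leave a serious event unreported that 7.2.2 requires, and nothing says which section prevails. Second, three of the seven types are also toxicities of the treatment under study. A retention, hematuria or erectile dysfunction of laser or mixed cause that appears after a biopsy could be left out of the IRB summaries and the stopping count, in a trial whose main purpose is safety.

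**Working it through.** **1. The sections side by side, for one listed event (post-biopsy urosepsis)**

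| Case | 7.2.3 | Other section |
|---|---|---|
| Serious, not fatal | Not reportable | 7.2.2: report, attribution irrelevant |
| Grade 5 | Not reportable, since no grade limit is set | 7.2.2: report, attribution irrelevant; 7.2.1: report the death within 7 days |
| Grade 3 or 4, for stopping | Not counted | Section 8: counted, no attribution condition |

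The first row is a direct contradiction: 7.2.3 exempts because of attribution, and 7.2.2 says attribution does not matter. The conflict with 7.2.1 is by implication only, because 7.2.3 names symptoms and reaches a death only through the missing grade limit. The third row is a failure to reconcile, since 7.2.3 could be meant as a carve-out that Section 8 omits to mention.

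**2. The plan's stopping probabilities**

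Inputs from Section 8: 15 patients; stop at 3 events (patients 3–5), 4 (6–10) or 5 (11–15). Assumption: at most one event per patient, with probability *p*.

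Let *a*ₙ(*k*) be the probability of having *k* events after *n* patients without having stopped. Then *a*ₙ(*k*) = (1 − *p*)·*a*ₙ₋₁(*k*) + *p*·*a*ₙ₋₁(*k* − 1) for *k* below the boundary, and P(stop) = 1 − Σₖ *a*₁₅(*k*).

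| Stopped by patient | *p* = 0.10 | *p* = 0.40 |
|---|---|---|
| 5 | 0.0086 | 0.3174 |
| 10 | 0.0176 | 0.6356 |
| 15 | 0.0237 | 0.8083 |

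The first row by hand: 10(0.1)³(0.9)² + 5(0.1)⁴(0.9) + (0.1)⁵ = 0.0081 + 0.00045 + 0.00001 = 0.00856. For 0.40: 0.2304 + 0.0768 + 0.01024 = 0.31744.

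The plan states 0.023 and 0.81 from 10,000 simulations. The simulation standard errors are √(0.0237 × 0.9763 / 10,000) = 0.0015 and √(0.8083 × 0.1917 / 10,000) = 0.0039, so both stated values lie within one standard error of the exact ones. They hold for whatever events are counted. What Section 8 does not say is whether the 0.1 and 0.40 are rates of all Grade 3 or 4 events or only of those attributed to the laser.

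**3. Timing**

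Inputs: follow-up biopsies at 12 and 24 months, each ± 1 month, with 36 months optional (3.4.2.3); accrual of about 6 months (3.1).

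- Earliest scheduled follow-up biopsy: 12 − 1 = month 11 after the first treatment.
- Gap after planned accrual closes: 11 − 6 = 5 months.
- Follow-up biopsy sessions if all patients are followed: 15 × 2 = 30, or 15 × 3 = 45 with the optional one. These are occasions on which the exemption could be applied, not expected events.

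On the planned timetable, all 15 patients are treated before any scheduled follow-up biopsy, so those biopsies can bear on early stopping only if accrual runs past 11 months. Clinically indicated biopsies could bear on it sooner. So, literally, could the pre-ablation screening biopsies, since 7.2.3 is not restricted to follow-up.

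**The case against.** **Scope.** The heading and opening of 7.2.3 confine it to events not considered secondary to the laser, so an event recognised as laser-caused falls outside it. This stands in part. But the text then sorts events by type and gives no way of deciding which cause applies. The investigator's review of each patient's adverse events in 7.4.1 does not supply one, and it refers back to the reporting requirements that conflict.

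**Deaths.** Sections 7.4.1 and 9.7 pause the study on any death and require its cause to be determined. This stands, and is why the 7.2.1 conflict is put no higher than an implication.

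**A separate biopsy protocol.** The biopsies run under another protocol, not available here, and their serious events may reach an IRB that way. That limits the practical harm. It does not satisfy a requirement in this protocol that disregards attribution. For the same reason no conflict is claimed with the 7.2.2 line on Grade 3 and 4 events related to the research.

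**Intended meaning.** Section 3.7.1.3 speaks of Grade 3 or 4 toxicity attributable to treatment, which suggests that laser-attributed events were meant. It governs stopping an individual procedure, and Section 8 does not repeat the condition.

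**Stronger readings the documents do not support.**

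- A reader might infer that late device effects are lost too, because 7.1.1 directs those "that occur more than 30 days after the last administration of investigational agent/intervention should be recorded and reported as per section 7.2". They are not: such an effect is by definition linked to the device and so lies outside 7.2.3, and the route through section 7.2 includes the 7-day reporting of unanticipated problems.
- A reader might treat all follow-up after the first biopsy as open to the exemption. That takes *post biopsy* to have no end, which is implausible for symptoms tied to a procedure, and the same logic would start the clock at the screening biopsy.
- A reader might infer a weakened stopping rule. If 25% of Grade 3 or 4 events were excluded at a true rate of 0.40, the counted rate would be 0.30 and P(stop) would be 0.53. The documents give no such share, so this illustrates sensitivity only.

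**Conclusion.** The concern holds as a contradiction in reporting obligations and an unresolved event definition for stopping. The conflict between 7.2.3 and 7.2.2 on serious and Grade 5 events is plain on the text. The conflict with 7.2.1 is by implication, and the Section 8 point is an ambiguity.

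The reporting conflict can arise at any biopsy during follow-up. Scheduled 12- and 24-month biopsies have little effect on early stopping if accrual takes the planned 6 months. The 30-day trigger in 7.4.1 (serious events in more than 2 patients) does not help with those biopsies, because it ends long before month 11.

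The stated 0.023 and 0.81 are correct as calculated. Nor does 7.2.3 remove events from data capture or from the toxicity frequencies in Section 8, and the IPSS and SHIM scores are untouched, so no planned endpoint analysis is shown to change. It should be fixed because it is safety-relevant and cheap to correct.

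**What to change.** 1. Reconcile 7.2.3 with 7.2.1 and 7.2.2, so that serious events, Grade 5 events and deaths after a biopsy are reported regardless of attribution.
2. Replace the exclusion by event type with case-by-case attribution, using the onset date and the date of the nearest biopsy, and state which role makes the judgement.
3. State in Section 8 whether the stopping count, and the 0.1 and 0.40 rates behind the stopping probabilities, refer to all-cause or laser-attributed events, and cross-refer to 7.2.3. Which definition to adopt is for the sponsor to decide; it has to be the same in both places.

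Cost: a few sentences in 7.2.3 and Section 8, two date fields, and slightly more IRB reporting. No new simulation is needed.

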## **7.2.4 NCI-IRB Reporting of Safety Reports**

Only Safety Reports that meet the definition of an unanticipated problem will need to be reported to the NCI IRB.

## **7.4 DATA AND SAFETY MONITORING PLAN**

### **7.4.1 Principal Investigator/Research Team**

The clinical research team will meet on a regular basis when patients are being actively treated on the trial to discuss each patient in detail.

All data will be collected in a timely manner and reviewed by the principal investigator or a lead associate investigator in a timely manner. Adverse events will be reported as required above. Any safety concerns, new information that might affect either the ethical and or scientific conduct of the trial, or protocol deviations will be immediately reported to the IRB using iRIS) and to the manufacturer.

In addition, the PI and associate investigators will monitor adverse events on an ongoing basis and modify the protocol and/or consent accordingly. After the first 5 patients are treated, and again after the first 10 are treated, interim assessments will be performed by the PI and associate investigators. This study will be stopped, and the IRB will be notified if adverse events develop which endanger patient safety, although the likelihood of this is so low that it is hard to create or imagine possible examples of such events.

The principal investigator will review adverse event and response data on each patient to ensure safety and data accuracy. The principal investigator will personally conduct or supervise the investigation and provide appropriate delegation of responsibilities to other members of the research staff. If there is mortality the study will be paused and a determination of cause will be pursued. If the cause was due to the laser therapy the pilot study will be concluded. Also, regarding other complications rates if the 30-day complication rate of serious events exceeds 2 patients a further analysis of the technique will be performed, as well as pausing and possible concluding the study if changes cannot be made for improvement.

## **8 STATISTICAL SECTION**

The primary goal of this study is to assess the toxicity, performance and feasibility of the Visualase thermal therapy procedure for focal prostate cancer treatment and then to monitor any complications for the 3 years following treatment. The outcome measures of importance during the thermal treatment are pain, frequency of thermal damage outside of intended treatment areas as measured by post contrast MRI, frequency of not completing the entire procedure, or the frequency of other adverse events and complications. These outcome measures are further defined as follows:

- \* Observing thermal damage on post contrast MRI which extends into areas of the Rectum or Urethra will be considered side effects for stopping purposes.
- \* Frequency of not completing the procedure. Not completing the procedure for reasons other than those given above will be considered a side effect for stopping purposes.
- \* Other adverse events or complications that occur that are classified as Grade 3 or 4 by the National Cancer Institute's Common Toxicity Criteria 4, will be considered a side effect for stopping purposes.

Sample size

The purpose of the study is to assess the safety, performance and feasibility of the Visualase thermal therapy procedure for focal prostate cancer treatment. The sample size is targeted at 15 evaluable patients which is adequate to assess the toxicity rate and can be reasonably recruited in a 6-month period of time. With the accrual of 15 patients, the width of the 80% expected confidence interval of 0.1 and 0.2 toxicity rate is 0.19 and 0.26, respectively.

Stopping rule

For the purpose of protecting patient safety, we implement the following stopping rule for safety monitoring. If one patient experiences a grade 5 event, thought to be possibly or probably due to the laser therapy, the study will be stopped. For grade 3 or 4 event, the study will be stopped according to the following stopping rule.

Number of patients	No. of grade 3 or 4 serious adverse events
3-5	3
6-10	4
11-15	5

The operating characteristic of the stopping rule was assessed by simulations. Based on 10,000 simulations, the probability of stopping early for an excess of serious adverse event over the course of trial is 0.023 when the serious adverse event rate is 0.1 and 0.81 when the serious adverse event rate is 0.40. This is deemed reasonable for protecting patient safety.

Frequency of the outcome measures, response and toxicity will be reported. Paired Student t test will be used to compare the difference between continuous variables (PSA, MRI imaging parameters) measured at baseline and at each follow-up visit. Prior to performing the paired t-test, the distribution of the underlying data will be assessed, and adequate transformation will be undertaken to ensure that the distribution of the transformed data is approximately normal. Descriptive statistics such as frequencies and percentages of categorical variables will be reported. In addition, McNemar's test, though may not have adequate power for this pilot study, will be explored to evaluate the difference in proportion between baseline and at each follow-up.

Longitudinal profiles of parameters recorded in the questionnaires over the course of follow-up for each patient will be plotted and the associated summary statistics such as mean, standard deviation, and mean change between successive follow-up visits will be reported. In addition, linear and non-linear mixed effects models will be explored to model the longitudinal profiles of the parameters of interest. In these models, random intercept will be used to incorporate the within-patient correlation of the repeated observations. If deemed appropriate, random slope will be added to the model to allow for the slope of profile to vary between patients.

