**3.7 CRITERIA FOR REMOVAL FROM PROTOCOL INTERVENTIONS AND OFF STUDY CRITERIA**

**3.7.1 Criteria for Stopping Laser Procedure**

During the laser procedure, outcome measures of importance that may interrupt or stop the procedure include the following:

- 3.7.1.1 Refusal to continue the treatment due to pain in spite of the opportunity to receive pain medication.
- 3.7.1.2 Observing thermal damage on post contrast MRI which extends beyond the estimated damage maps from the Visualase software or which extends into areas of the Rectum or Urethra will be considered side effects for stopping purposes.
- 3.7.1.3 Grade 3 or 4 toxicity attributable to the treatment.
- 3.7.1.4 Patient choice for reasons other than those given above.
- 3.7.1.5 The investigator feels it is in the best interest of the patient.

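### Section 8 labels rectal or urethral thermal damage and non-completion as stopping events, but the study stopping table counts only grade 3 or 4 serious adverse events

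*Combined protocol and SAP*

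**What the plan says.** Section 8 lists outcome measures for the thermal treatment and then defines three of them by bullet. Each bullet carries the stopping label:

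- Damage: "Observing thermal damage on post contrast MRI which extends into areas of the Rectum or Urethra will be considered side effects for stopping purposes".
- Non-completion: "Not completing the procedure for reasons other than those given above will be considered a side effect for stopping purposes".
- The rest: "Other adverse events or complications that occur that are classified as Grade 3 or 4" under the NCI toxicity criteria.

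The first two bullets require no toxicity grade, and the third opens with a word that sets it apart from them.

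The stopping rule follows in the same section. One grade 5 event possibly or probably due to the laser stops the study. For non-fatal events there is a table whose count column is headed "No. of grade 3 or 4 serious adverse events". Its limits are 3 events among 3 to 5 patients, 4 among 6 to 10, and 5 among 11 to 15. The operating characteristics come from 10,000 simulations: "the probability of stopping early for an excess of serious adverse event over the course of trial is 0.023" at a serious adverse event rate of 0.1, and 0.81 at a rate of 0.40.

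Two other places bear on the point. Section 3.7.1.2, which concerns stopping the laser procedure, uses the same label for damage: "or which extends into areas of the Rectum or Urethra will be considered side effects for stopping purposes". Section 7.4.1, repeated in 9.7, adds a second numeric trigger for non-fatal events: "if the 30-day complication rate of serious events exceeds 2 patients a further analysis of the technique will be performed".

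**The concern.** Two of the three event classes that Section 8 declares relevant to stopping do not appear in the rule that decides stopping. The third is the very event the table counts, so the label is most naturally read at study level for all three.

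The damage class matters most. Heating of the rectum and urethra is the hazard that the automatic shut-off at 45°C in Section 3.2.2.2 is there to prevent, and post-contrast MRI is how the plan would see that the safeguard had failed. Such a finding may be asymptomatic or low grade. Investigators and the IRB applying the table as printed would not count it, although the bullets a few lines earlier say it bears on stopping.

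**Working it through.** **1. What reaches the table**

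| Event in Section 8 | Stopping label | Counted in table | Covered by 0.023 and 0.81 |
|---|---|---|---|
| Rectal or urethral MRI damage below grade 3 | yes | no | no |
| Non-completion without a grade 3 or 4 event | yes | no | no |
| Grade 3 or 4 serious adverse event | yes | yes | yes |

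No rate has to be assumed to see the consequence. Damage below grade 3 in 5 men, or in all 15, gives a table count of 0, whereas 5 table events stop the study. The 30-day trigger in 7.4.1 acts at 3 patients with serious events and names neither omitted class.

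**2. Reproducing the plan's figures**

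Inputs from Section 8: 15 patients; limits 3, 4 and 5; per-patient event rate p = 0.10 or 0.40. I allow at most one event per patient and stop when the count reaches the limit. The limit is constant within each band and the count cannot fall, so it is enough to check after 5, 10 and 15 patients:

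P(stop) = 1 − P(S5 ≤ 2, S10 ≤ 3, S15 ≤ 4), where each block of five patients is Binomial(5, p).

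At p = 0.10:
- After 5 patients, not stopped with 0, 1 or 2 events: 0.59049, 0.32805, 0.07290.
- After 10, not stopped with 0, 1, 2 or 3 events: 0.34868, 0.38742, 0.19371, 0.05261.
- Chance that the last five add no more than 4, 3, 2 or 1 events: 0.99999, 0.99954, 0.99144, 0.91854.
- Products: 0.34867 + 0.38724 + 0.19205 + 0.04833 = 0.9763 not stopped, so P(stop) = 0.0237.

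At p = 0.40 the same steps give 0.00598 + 0.03680 + 0.08254 + 0.06641 = 0.1917 not stopped, so P(stop) = 0.8083.

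The plan states 0.023 and 0.81. The Monte Carlo standard errors are √(0.023 × 0.977 / 10,000) = 0.0015 and √(0.81 × 0.19 / 10,000) = 0.004, so both figures reproduce. Reading the limits as counts to be exceeded gives 0.0034 and 0.614, which does not match.

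**3. If damage is counted as well**

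The probability depends only on the per-patient rate of a counted event. The documents give no damage rate x, so 2% and 5% are assumptions. With independence, p = 1 − (1 − base)(1 − x). With no overlap, p = base + x. With complete overlap, p = base.

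| Base rate | Damage x (assumed) | Overlap | p | P(stop) |
|---|---|---|---|---|
| 0.10 | any, up to 0.10 | complete | 0.10 | 0.0237 |
| 0.10 | 2% | independent | 1 − 0.90 × 0.98 = 0.118 | 0.0411 |
| 0.10 | 2% | none | 0.12 | 0.0434 |
| 0.10 | 5% | independent | 1 − 0.90 × 0.95 = 0.145 | 0.0797 |
| 0.10 | 5% | none | 0.15 | 0.0885 |
| 0.40 | 2% | independent | 1 − 0.60 × 0.98 = 0.412 | 0.8325 |
| 0.40 | 5% | independent | 1 − 0.60 × 0.95 = 0.430 | 0.8647 |

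**4. If non-completion were added too**

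At base 0.10, with damage and non-completion independent and at the same assumed rate:
- 2% each: p = 1 − 0.90 × 0.98 × 0.98 = 0.136, P(stop) = 0.0645.
- 5% each: p = 1 − 0.90 × 0.95 × 0.95 = 0.188, P(stop) = 0.1724.

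**The case against.** The strongest reply is that the label refers to stopping the individual laser procedure. Section 3.7.1.2 uses it for damage under exactly that heading. Sections 3.7.1 and 8 open their lists in nearly the same way, as outcome measures during treatment. Section 3.7.1.3 lists "Grade 3 or 4 toxicity attributable to the treatment" much as the third bullet of Section 8 does. The study-level rule then stands under its own heading with its own event.

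For damage, this leaves the intent arguable. It is weakened by Section 3.2.2.2, which schedules the contrast-enhanced images after all laser treatments, when there is normally no procedure left to stop. For non-completion the reading fails, because a procedure that was not completed cannot be a reason to stop itself.

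The second reply is that other safeguards exist, and they do. Section 7.4.1 provides review of each patient, interim assessments after 5 and 10 patients, immediate reporting of safety concerns to the IRB and the manufacturer, and stopping if adverse events endanger patients. Its 30-day trigger does not define serious by grade, so a rectal injury judged serious could count. A reader might infer that MRI damage would go unnoticed or unreported; the documents do not support that. What is missing is a number.

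Third, weighting an asymptomatic MRI finding like a grade 3 or 4 event is partly a clinical choice, and the sizes in the working rest on assumed rates. Both points stand. The mismatch itself depends on neither.

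**Conclusion.** The point holds as a mismatch between the events Section 8 declares relevant to stopping and the events its rule counts. MRI damage below grade 3 and non-completion have no limit in the table and no part in its operating characteristics. That follows from the text alone.

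Three stronger conclusions might be drawn and should not be:
- That 0.023 and 0.81 are wrong. They are correct for a single event type counted once per patient.
- That the sponsor certainly meant damage to count toward stopping the study. The study-level reading is the better one, but Section 3.7.1.2 leaves room for the other.
- That the rule ignores attribution. Section 3.7.1.3 speaks of treatment-attributable toxicity and Section 7.2.3 keeps biopsy symptoms out of the study's stopping criteria.

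The effect of counting damage is modest over the assumed range. At a 0.10 serious-event rate, stopping goes from 0.024 to between 0.024 and 0.043 for 2% damage, and to between 0.024 and 0.089 for 5%, depending on overlap. At 0.40, with independence, it goes from 0.81 to 0.83 or 0.86. This merits a correction because the trial's primary question is safety and the remedy is cheap.

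**What to change.** Amend the wording of Section 8 as follows.

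- **Stopping rule.** Define the counted event as a patient with rectal or urethral thermal damage on post-contrast MRI, a grade 3 or 4 event, or both. Each patient counts once. Keep the limits of 3, 4 and 5, and change the table heading to match.
- **Operating characteristics.** State that 0.023 and 0.81 apply when the composite per-patient rate is 0.10 and 0.40. No new simulation is needed for these two figures.
- **Non-completion.** Remove the stopping label from that bullet and report non-completion as a feasibility frequency, which the primary objective already calls for. Counting it would put the chance of stopping at a 0.10 serious-event rate at 0.06 or 0.17 under the assumed 2% or 5% rates for each class.

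The cost is a somewhat higher chance of stopping when serious events are at the 0.10 rate: about 0.04 or 0.08 instead of 0.024 for an assumed independent damage rate of 2% or 5%, and no change with complete overlap. Sample size, visits and imaging are unaffected.
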